Essex Coronavirus Action Support (ECAS) involves collaboration between Essex County Council (ECC) and The Essex Public Health Team as well as local Facebook groups. It focuses on the provision of three services: *preventing* the spread of infection, *informing* Essex residents of guidance and *assisting* residents who may be vulnerable. The ECAS Facebook page which was created on 14th March 2020 ('Essex Coronavirus Action', 2020) is now followed by 55,339 people (at the time of writing) and is used to distribute information to the community. The related private group created on 15th March 2020 has approximately 37,900 members ('Essex Coronavirus Action Support', 2020) and is described as a space for residents of Essex, promoting connection and discussion about issues related to the COVID-19 pandemic.

When membership of the ECAS group is requested, admins ask for a postal code to verify people are Essex residents, members are not actively recruited. Whilst approximately 80% of the demographic is female, men have been reported to be over-represented in discussion ('Mobilizing Essex residents', 2020). There are 18 community admins who oversee the private group, three have a prominent role with ECC paying for their work. Issues around misinformation are dealt with on a case-by-case basis and in rare instances members are banned/ muted if promoting argument.

Growth, recruitment and management have been described as evolving intuitively and some research has been conducted to capture decisions explicitly in terms of team roles, structure and the organisational environment ('Essex County Council', 2021). The co-produced logic model illustrating resources, activities and outcomes as well as their connection (shown in Figure 1) guides the current evaluation of the ECAS intervention.

The proposed evaluation will combine quantitative (Work Package 1, see *Methods* below) and qualitative (Work Package 2) methods to understand the extent to which ECAS achieved its aims to facilitate 'prevent, perform and assist' and also the wider impact it has had on public health system approaches.

Rationale

Promoting behavioural change

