COVID protective behaviours	Engage in behaviours which are likely to reduce infection risk to self and others	Self-report (critical phase)	Items from Freeman et al. (2020)
Community champion activity	Helped others practically in real world Signposted to online reliable information Corrected misinformation online	Self-report (critical phase)	Study generated scale
Mental health	Level of anxiety Satisfaction with life COVID specific anxiety syndrome	Self-report (critical phase)	GAD-7 (7 items) PHQ-9 (9 items) SWLS (~5 items) Nikčević & Spada (2020)
	Level of anxiety	Self-report (current state)	GAD-7 (7 items)

¹ Use of tools is subject to securing permissions, where required, from authors.

The relationships highlighted in Figure 2 will be analysed using the Hayes PROCESS macro tool (Hayes, 2018), focusing on one effect and mediation per model (see power analysis below for a rationale).

This aspect of the research will also take additional *secondary outcome measures* from those who engaged with ECAS including *sense of ownership of the site* (self, community, local authority), *understandings of information provenance*, *confidence in information*, *frequency of referrals made to the site* and *reliance upon site*. This will allow exploratory testing of how these factors relate to the efficacy of the intervention. These will need to be short measures (i.e., single item scales) given the length of the primary outcome measures and subsequent possible impact upon participant attrition.

Analysis of existing data

Social network analysis: We will explore the feasibility of using social network analysis (SNA) to see the extent to which influence (categorised as interactions) in the network is central (via admins out to members) or distributed (member to members, including core member and peripheral members) over a given time period (see *Sampling*, below). Data will be analysed using the SNA package on R.

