Work Package 1: We will aim to recruit a sample of $n = 225$ people who have signed up to the ECAS Facebook page and group. We will also recruit a comparative, equally sized sample of Facebook users who did not sign up to the page nor recall being exposed to it. These will be either a comparative demographic profile, or we will weight responses to match our samples. Recruitment will be conducted via Facebook. The total target sample size will be $n = 450$. See *Recruitment*, below, for details on how these samples will be secured.

Inclusion criteria:

- 18+ years of age
- Facebook user
- Enrolled in ECAS page and group on Facebook (ECAS condition only)
- Works or lived in Essex during first lockdown period

Exclusion criteria:

- Enrolled in ECAS page and group on Facebook (comparator condition only)
- Unable to give informed consent

Social network analysis: Data will be collected from the ECAS group page drawing on posts made (i) during the first two weeks of the first lockdown and (ii) the first two weeks following the lifting of the first lockdown. In each period, the highest day traffic will be selected, then the lowest (non-contiguous) day and then the non-contiguous day closest to the mean. We will manually sample and code 800 contiguous interactions per day, three days per phase (total $n = 2400$ interactions).

Size of sample

Primary analysis sample: Our within condition sample of $n = 225$ allows detection of single mediation effects at power = 0.81 assuming medium (Pearson $r = .30$) relationships between variables (calculated using 'pwr2ppl' R package 'med' function). In the absence of suitable pilot data, these levels of relationship have been selected as they represent effects which are likely, and are in line with relationships between social identity and efficacy and behaviour observed in other studies (i.e., Frings, Wood & Albery, in press). Relationships smaller than that powered for are also likely to be of less practical significance. A sample sufficient to power multiple mediation models is beyond the scope of the current study.

Social network analysis: This sample size indicated above balances a manageable amount of data inputting and sufficient data to generate meaningful insight. Focusing on high and low traffic days gives a representation of time the group is seeking and receiving information from the centre of the network and times when they are engaged in more general interaction.

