Qualitative component 2: semi-structured interviews: The key ethical risk here is that participants will be asked to recall experiences which occurred over lockdown, which may be upsetting for people. We will mitigate this by fully informing participants of the content of the study in advance and providing support and debriefing if necessary during the interview.

Assessment and management of risk

Table 3: Risk register

Key risk	Likelihood	Impact on participants	Impact on project	Mitigation
COVID19 interferes with staff availability (research team + stakeholders)	Moderate	N/A	Moderate	Depth of team, clear project planning to facilitate handover, lines of alternative communication established, agreement to support the evaluation through a Memorandum of Collaborations between LSBU and ECC
Failure to recruit to quantitative strand	Moderate	N/A	High	Guidance from PPIE in planning stage Leverage market research panel resources
Data not available from partners	Low	N/A	Moderate	Agreement with partners on data, ongoing stakeholder involvement Agreement in place to support the evaluation through a Memorandum of Collaborations between LSBU and ECC

Amendments

Significant amendments to the protocol will be discussed in advance with the PHIRST London Central Executive Committee and PH Essex. Should these discussions suggest a need for consultation with the NIHR, this will be co-ordinated by PHIRST London.

Peer review

This protocol will receive a proportionate review by PHIRST London and the NIHR.

Patient & Public Involvement and Engagement

The workshops that informed this design were attended by three Essex community members who have been involved in the development and implementation of ECAS. As these members also received a financial recompense from ECC for their involvement, we extended our PPIE strategy to establish a PPIE Advisory Panel made up of ECAS users and Community Admins involved on a voluntary basis. The project aims to have in place a PPIE Advisory Panel of five members in total. Recruitment was undertaken through advertising on the Facebook page and targeted recruitment for Admin. Three panel members have been active so far and further recruitment is ongoing.

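### The Work Package 1 criteria neither exclude nor identify the people who deliver ECAS, whose role overlaps engagement and part of one outcome, community champion activity

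*Protocol*

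**What the plan says.** Under Samples and recruitment (Sampling, Work Package 1), the ECAS sample must be aged 18 or over, use Facebook, be "Enrolled in ECAS page and group on Facebook (ECAS condition only", and meet the Essex criterion, "Works or lived in Essex during first lockdown period". Of the two exclusions, one applies to the comparator only. The one that reaches the ECAS sample is "Unable to give informed consent". The target is 225 per sample. Sampling technique and Recruitment describe a convenience sample, recruited by posts in the ECAS group and encouraged by vouchers.

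The intervention of interest (Background) says that the private group "has approximately 37,900 members" and that "There are 18 community admins who oversee the private group, three have a prominent role with ECC paying for their work".

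Table 1 measures exposure as engagement or not and, among users, its intensity. One of the three interim outcomes, community champion activity, is a study-generated self-report scale with three components: "Helped others practically in real world Signposted to online reliable information Corrected misinformation online". The other two interim outcomes are digital health literacy and COVID protective behaviours.

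Elsewhere the protocol does separate admins from members. The social network and discourse analyses distinguish influence flowing from admins to members from influence between members, and Work Package 2 interviews admins alongside council and public health staff.

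**The concern.** The within-ECAS analysis asks whether members who engage more are better connected and do more of the intended behaviours. For someone who runs the group, high engagement is part of the role. So, on a natural reading, are pointing people to reliable information and dealing with misinformation, which the Background describes directly after the admins. For these respondents, exposure and two components of one outcome partly record the same work. A small cluster that is high on both variables produces a positive correlation even if engagement does nothing for ordinary members.

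The error runs in one direction, in favour of ECAS. The safeguard in Sampling technique would not reveal it: the comparison with the ECAS and Essex populations is described as demographic, and role is not part of it. If role is not recorded, the effect cannot be examined afterwards.

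**Working it through.** **Inputs from the protocol.** ECAS sample n = 225; planned correlations r = .30; stated power 0.81; 18 admins; about 37,900 group members. **Assumptions.** Two-sided 5% test (the protocol states no level); k deliverers among the 225; a shift of d SD on both engagement and champion activity; no true association in anyone else. The protocol gives neither k nor d.

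**1. The stated power reproduces.** Sobel test on standardised paths:
- a = .30; b = (.30 − .09)/(1 − .09) = .231; R² = (2 × .09 − 2 × .027)/.91 = .138.
- SE(a) = √(.91/223) = .0639; SE(b) = √(.862/(.91 × 222)) = .0653.
- z = ab/√(a²·SE(b)² + b²·SE(a)²) = .0692/.0245 = 2.82, so power = Φ(2.82 − 1.96) = 0.806, in agreement with 0.81.

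The point below does not touch this figure.

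**2. How many deliverers to expect.** A random draw would contain 225 × 18/37,900 = 0.11 admins. If all 18 responded they would be 18/225 = 8% of the sample. Self-selection through posts in the group they run puts the number somewhere in between; the documents do not say where.

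**3. Induced correlation.** With p = k/225 and q = p(1 − p), r = q·d²/(1 + q·d²). Example, k = 5 and d = 2: q = .0222 × .9778 = .0217; r = .0869/1.0869 = .080. The significance threshold at n = 225 is r = .131. Each cell gives the induced r and, in brackets, the simulated false-positive rate (10,000 runs):

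| k | d = 1 | d = 2 | d = 3 |
|---|---|---|---|
| 3 | .013 (0.050) | .050 (0.115) | .106 (0.355) |
| 5 | .021 (0.063) | .080 (0.225) | .164 (0.698) |
| 8 | .033 (0.083) | .121 (0.448) | .236 (0.956) |
| 18 | .069 (0.175) | .227 (0.942) | .398 (1.000) |

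Smallest k for the induced r to reach .131: 42 at 1 SD, 17 at 1.5, 9 at 2, 6 at 2.5 and 4 at 3. Smallest k to reach the planned .30: 28 at 2 SD (more than the 18 admins), 17 at 2.5 and 12 at 3.

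**4. Planned mediation test.** The protocol names the PROCESS macro but not the interval, so two tests were simulated (4,000 runs), with social connection also shifted by d:

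| k, d | Sobel | Both paths significant |
|---|---|---|
| 5, 2 SD | 0.6% | 3.8% |
| 8, 2 SD | 4.1% | 15.6% |
| 5, 3 SD | 17% | 39% |
| 8, 3 SD | 64% | 79% |
| 18, 2 SD | 56% | 75% |

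If social connection is not shifted, spurious mediation stays below 0.5% in every case run.

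**5. Difference from the comparator.** The ECAS mean rises by (k/225)·d. At d = 2 this is 0.044 SD for k = 5 and 0.16 SD for k = 18. Against a standard error of √(2/225) = 0.094, that is about 0.5 and 1.7 standard errors.

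**The case against.** The strongest reply is that everything quantitative rests on two unknowns. A reader might infer that a few deliverers would be enough to create the engagement-outcome association. The documents do not support that. Five people at 2 SD give r = .08, below the threshold; a handful suffices only at about 2.5 to 3 SD; and no small number reaches the planned .30. The planned analysis is also a mediation model, which 5 deliverers at 2 SD leave within the nominal 5%. All of this stands.

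Three further limits also stand:
- The role overlap concerns one of three interim outcomes. Health literacy and protective behaviour are not described as admin duties, and practical help in the real world, the first component of champion activity, is not a moderation task. Nothing shows admins to be extreme on social connection.
- A reader might count the patient and public panel and council staff as further groups of deliverers. The panel is a "PPIE Advisory Panel made up of ECAS users and Community Admins involved on a voluntary basis", so it partly overlaps the 18 admins, and a user on it is a recipient. The protocol does not say how many council or public health staff are enrolled, if any. The paid people it counts are three of the 18 admins.
- The comparator is recruited through other community groups, whose own moderators are eligible and may do similar work. That would offset part of the between-sample shift.

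It can also be said that influence checks belong in an analysis plan. That is fair for the analysis, but eligibility is fixed here, and no later analysis can use a role that the survey did not record.

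**Conclusion.** The gap is certain on the text: the criteria admit the people who run ECAS, and nothing flags or separates them. The consequence is narrower than that might suggest. Their inclusion can inflate the association between engagement and community champion activity and, slightly, the ECAS-comparator difference on that outcome. With no true association, the false-positive rate for the correlation is about 6% with 5 deliverers at 1 SD, 23% at 2 SD and 70% at 3 SD, against a nominal 5%. Uptake, shift and test level are assumptions. The contribution of the two overlapping components to a scale still to be written is also unknown. The documents do not support extending the concern to all outcomes, to the mediation result in general, or to every panel member. This is a cheap improvement that removes a one-directional bias, not a flaw that invalidates the design.

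**What to change.** Add one question on role in ECAS to the Work Package 1 survey. Exclude from the ECAS sample current or former ECAS admins and moderators, and council or public health staff who deliver ECAS. Replace them so that n stays at 225. At minimum, keep the role question and pre-specify the analysis without these respondents. Ordinary ECAS users on the patient and public panel need only be flagged.

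The cost is one survey item, one exclusion line and a few ineligible people out of about 37,900 members. With replacement, power stays at 0.81. Without it, the Sobel calculation gives 0.797 if 5 are removed (n = 220) and 0.772 if all 18 admins are removed (n = 207). The deliverers' views are not lost, because Work Package 2 already plans interviews with 6-8 admins, 5-6 council staff and 6-8 public health staff.

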Effects of ECAS and underlying processes: For those that have joined ECAS, we will test how engagement with the ECAS Facebook page and group relates to (i) a sense of social connection and (ii) how both engagement and the sense of social connection relate to the interim outcomes of increased health literacy, covid protective behaviour and community champion activity (see Figure 2). A further analysis will compare levels of each of these factors amongst those who did engage with the intervention versus a comparator group who did not and across socio-demographic groups if the data allows (i.e., using moderation analyses). Amongst both samples, we will also measure current levels of mental health and test relationships between these and each factor. These analyses will provide a quantitative evaluation of the extent to which the intervention met its aim to ‘inform’, ‘prevent’ and ‘assist’. Additionally, for those who engage in it, it will also identify which interim outcomes were most impacted and the extent to which this effect was mediated by social connection.

[figure not shown]

Figure 2: Primary conceptual model to be tested.

Given the nature of the study, much of these data will be retrospective (i.e., people’s recollection of their behaviours). In these instances, we will ask participants to recall how they felt during what our preparatory work with stakeholders (stakeholder workshops and also a PPIE workshop), identified as a *critical phase* of the intervention’s deployment. The critical phase selected for the quantitative analysis of new data is the the first two weeks following the lifting of the first lockdown.

Table 1 (see below) indicates broad operationalisations of each of the factors, the source of data (and whether it is current or retrospective) and possible measurement instruments.

Table 1: Indicative primary outcome measures¹

Factor	Operationalisation(s)	Source of data	Indicative instrument
Interaction with ECAS	Did / did not engage with site Intensity of engagement (users only)	Facebook data or self-report	Study generated scale/metrics
Social connection	Sense of social connection with others Collective responsibility	Self-report (current) Self-report (critical phase)	Validated scale (Lee, Draper & Lee, 2001)
Health literacy	Level of perceived digital health literacy	Self-report (current)	Use of two subscales: information searching and evaluating reliability from validated scale (Van der Vaart & Drossaert, 2017)

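### The ECAS group is defined by enrolment at any date, so members who joined after the critical phase are analysed as ECAS participants for outcomes that preceded their joining

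*Protocol*

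**What the plan says.** **Who is in the ECAS arm.** Under Samples and recruitment, the target is 225 "people who have signed up to the ECAS Facebook page and group", and the matching inclusion criterion is "Enrolled in ECAS page and group on Facebook (ECAS condition only"). Enrolment is also the exclusion criterion for the comparator arm. The only dated criterion concerns place, not membership: "Works or lived in Essex during first lockdown period". Recruitment is by posts to the group as it stands when the survey runs. The Milestones table lists data collection for completion in November 2021. The private group opened on 15 March 2020.

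**When the outcomes occurred.** Under Primary analyses of new data, the Protocol says that "much of these data will be retrospective (i.e., people’s recollection of their behaviours"), and that such items will refer to a critical phase, namely "the first two weeks following the lifting of the first lockdown". Table 1 assigns to that phase:
- COVID protective behaviours ("Engage in behaviours which are likely to reduce infection risk to self and others");
- community champion activity (for example, "Helped others practically in real world");
- part of the social connection factor;
- the main mental-health row (GAD-7, PHQ-9, SWLS and COVID anxiety).

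Digital health literacy, the other part of social connection and a second GAD-7 are current-state measures.

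**When exposure is measured.** The source entry for interaction with ECAS is "Facebook data or self-report". It is the only row of Table 1 that is marked neither current nor critical phase.

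**The concern.** Exposure should precede the outcome it is meant to explain. The Protocol's own Table 2 samples group discussion in a second lockdown (October to November 2020) and a third (January 2021), so the group was active well after the first lockdown ended. Someone who joined in either period meets every ECAS criterion, yet was not a member when the critical-phase outcomes occurred. The same person is barred from the comparator arm, although during the outcome window their membership status was that of a comparator.

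Three analyses are touched:
- **ECAS versus comparator.** On critical-phase outcomes the contrast becomes ever joined by 2021 against never joined.
- **Mediation models within the ECAS sample.** If engagement has no time limit, its intensity can include activity after the outcome, even among early joiners.
- **Cost per unit of change.** The economic evaluation reuses the Table 1 outcomes and the same comparator.

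Two of the three named interim outcomes, protective behaviour and champion activity, belong to the critical phase.

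**Working it through.** **1. Timing, side by side**

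| Element | Reference period in the Protocol |
|---|---|
| ECAS membership | Any time from 15 March 2020 until the survey |
| Engagement (did or did not; intensity) | None stated |
| Protective behaviours, champion activity, main mental-health row, part of social connection | Two weeks after the first lockdown lifted |
| Digital health literacy, rest of social connection, second GAD-7 | Current at survey |

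Nothing in the Protocol collects a join date, limits engagement to the critical phase, or separates later joiners in the analysis. It also gives no calendar dates for the critical phase.

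**2. The Protocol's own power figure**

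Inputs from Size of sample: n = 225, all correlations .30, stated power 0.81. Alpha is not stated; two-sided 0.05 is assumed. Using a Sobel test of the indirect effect:
- a = .30; b = (.30 − .30 × .30)/(1 − .09) = .21/.91 = .231
- R² of the outcome on engagement and connection = 2 × .231 × .30 = .138
- SE(a) = √(.91/223) = .0639; SE(b) = √(.862/(.91 × 222)) = .0653
- z = ab/√(a²SE(b)² + b²SE(a)²) = .0692/.0245 = 2.82
- power = Φ(2.82 − 1.96) = 0.806 (0.811 with n in both denominators)

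The stated 0.81 is reproduced. The sample-size calculation is not wrong, but for critical-phase outcomes it implicitly takes all 225 as exposed before the outcome.

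**3. Group contrast, illustration only**

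The Protocol gives neither the share q of late joiners nor an effect size for this contrast. Assume q from 10% to 40%, a true d = 0.30, and no effect in late joiners, who otherwise resemble comparators. The diluted effect is d(1 − q), and power ≈ Φ(d(1 − q)√(225/2) − 1.96).

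| q | Diluted d | Power (normal) | Power (t-test) |
|---|---|---|---|
| 0 | 0.30 | 0.889 | 0.888 |
| 10% | 0.27 | 0.817 | 0.815 |
| 20% | 0.24 | 0.721 | 0.719 |
| 30% | 0.21 | 0.605 | 0.604 |
| 40% | 0.18 | 0.480 | 0.478 |

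**4. Mediation models, illustration only**

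The result depends on which correlations late joiners weaken. If both engagement–outcome and connection–outcome correlations become .30(1 − q) while engagement–connection stays .30, Sobel power is 0.74, 0.66, 0.56 and 0.46 for q = 10% to 40%. If only engagement–outcome is weakened, b increases and power for the indirect effect rises to 0.82, 0.84, 0.85 and 0.87. The Protocol does not say which pattern applies, so the direction is not fixed.

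**5. Price of restricting the sample**

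Removing 10%, 20% or 30% from a fixed 225 leaves 202, 180 or 158. The calculation in step 2 then gives power 0.76, 0.71 or 0.66. Keeping 225 eligible members needs 225/(1 − q) ECAS respondents: 250, 282 or 322.

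**The case against.** The strongest reply is that eligibility is not exposure. Enrolment decides who may answer the survey, while Table 1 measures engagement separately, and the main models run on measured engagement. The text on retrospective data says recalled behaviours will be asked for the critical phase. Past engagement could fall under that rule, and Table 1 is described as indicative. A questionnaire with such a stem would score a later joiner as not engaged. This stands for the within-ECAS models, where the defect is an unstated period and not a stated decision to count later activity. It does not protect the ECAS-versus-comparator contrast if arms follow the recruitment definition, because a time stem alone does not move a late joiner out of the ECAS arm.

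The second reply is that later joiners may already have seen ECAS content. Enrolment requires both the page and the private group, the page distributed information to the community, and ECAS also posted on Instagram and Twitter. This stands too: no effect at all in late joiners is an extreme assumption.

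A reader might infer that the contrast is necessarily diluted, so that a null result would be explained by late joiners. The document does not support that. Late joiners may have differed from comparators in earlier behaviour, and that behaviour may have prompted joining, so bias could run either way. Nor does it show that late joiners are numerous. The residence criterion, tied to the lockdown and not to the fortnight after it, might look like a second mismatch. The two periods adjoin and no material movement out of Essex is shown, so it is minor.

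**Conclusion.** The point holds for critical-phase outcomes. As written, the Protocol places members who joined after the outcome window in the ECAS arm, and it leaves the period of engagement open. That can bias the group contrast and, unless engagement is asked for the critical phase, the mediation models.

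Size and direction cannot be determined from the document. The fall in power from 0.89 to between 0.82 and 0.48 illustrates one scenario. It rests on an assumed d = 0.30, an assumed 10% to 40% late joiners, and no effect in them. It is not an estimate of the loss in this study. The contrast itself has no stated power in the Protocol, and the stated 0.81 for mediation is arithmetically sound.

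Current digital health literacy, current social connection and current GAD-7 are not affected. The matter belongs in the Protocol because eligibility and exposure are fixed there. A join date that is never collected may not be recoverable from an anonymised survey, so no later analysis plan can be relied on to supply it.

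**What to change.** 1. State the calendar dates of the critical phase.
2. Add a self-reported item on when the respondent joined ECAS.
3. Give the engagement measure a reference period, up to and including the critical phase, for use with critical-phase outcomes.
4. Restrict the primary analyses of critical-phase outcomes to members enrolled before that phase began. Analyse later joiners separately as a sensitivity group, and keep them in the analyses of current-state outcomes.
5. State that the 0.81 power applies to 225 members enrolled before the critical phase.

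The cost is one survey item, a time stem, some recall error in the join date, and fewer people in the critical-phase analyses. With recruitment held at 225, mediation power would be about 0.76, 0.71 or 0.66 if 10%, 20% or 30% joined late. Holding it at the planned level would instead mean recruiting about 250, 282 or 322 ECAS respondents.

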All research will be conducted in line with LSBU ethics panel code of conduct for research involving human participants and the British Psychological Society's ethical guidelines. These guidelines include principles of holding participants rights and dignity, anonymity, and freedom to choose to participate or not. Research will also be conducted and reviewed the way which makes it compliant with GDPR (or replacement legislation). Each strand of the research presents a number of particular ethical risks.

Work Package 1:

New data analysis sample: The key ethical risk here is that participants will be asked to recall experiences which occurred over lockdown, which may be upsetting for people. We will mitigate this by fully informing participants of the content of the study in advance.

Social network analysis: The key ethical consideration for this strand of the research is around use of data without participants' explicit consent. Our initial PPIE work has indicated

that such a use would be considered reasonable, data will be anonymised at source and only the source, target and length of interaction will be recorded. We will continue to engage with our PPIE group as this work develops. This issue is also more fully explored in ethical considerations for Work Package 2 (see next section).

Work Package 2:

Qualitative component 1: Participant observation of Facebook interactions analysed using discourse analysis: The key ethical consideration here is the detailed analysis of Facebook postings without participants' explicit consent. LSBU code of practice for human research recognises the need for consent in such studies, but also recognises the principle of fair processing and the need for judgement about the extent the use has the potential to cause distress (LSBU Code of Practice for Human Research, 2020, sections 2.1 and 2.2). Feedback from our PPIE work on this issue confirms that this would be reasonable if the data were anonymised. Feedback also suggested that, although the Facebook group is technically a closed group, it was described as a 'semi-public' space because there are 38,000 members. Furthermore, the only reason that the group is closed is based upon the geographical catchment area. Permission from the site owners/moderators will be obtained.

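### The survey's work-or-residence criterion lets people who only work in Essex into the comparator, while the ECAS sample comes from a group that checks Essex residence

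*Protocol*

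**What the plan says.** Protocol, Samples and recruitment, Sampling: the survey is to recruit 225 ECAS members and 225 comparators. Four statements there fix who can enter.

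- Geography, not tied to either condition: "Works or lived in Essex during first lockdown period".
- Membership, tied to the ECAS condition: "Enrolled in ECAS page and group on Facebook (ECAS condition only").
- Exclusion, tied to the comparator: "Enrolled in ECAS page and group on Facebook (comparator condition only").
- Comparator description in the text: "Facebook users who did not sign up to the page nor recall being exposed to it".

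The intervention of interest describes two Facebook components. The page is followed by 55,339 people and distributes information. The private group is "described as a space for residents of Essex", and on a request to join, "admins ask for a postal code to verify people are Essex residents". The ethics section (discourse analysis in Work Package 2) adds that "the only reason that the group is closed is based upon the geographical catchment area".

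For balance between the samples, Sampling offers a comparable demographic profile or weighting. Sampling technique adds that the health equity analysis will show whether the samples represent ECAS users and the Essex population, and that weighting will be explored if they do not. Neither place lists its variables or mentions residence. Recruitment brings comparators in through community Facebook groups and paid posts, with no residence screen stated.

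**The concern.** The same criterion has different effects in the two samples. Its work limb widens the comparator to people living outside Essex. It adds almost nobody to the ECAS sample, because entry to the private group already turns on residence.

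The comparison of interest is between people who could have been in the ECAS condition and were, and people who could have been and were not. Work-only comparators fall outside that second group. If residents and non-residents differ on the outcomes, part of any observed difference reflects where people live.

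Two analyses use this comparator. Primary analyses of new data compares social connection, health literacy, protective behaviour and community champion activity between ECAS users and comparators. Work Package 3 sets costs and cost-effectiveness against the same comparator, in the first instance from the perspective of the local authority and its public health team.

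**Working it through.** **1. The plan's own figure.** Size of sample states power 0.81 for a single mediation effect with n = 225 and correlations of .30. Alpha and sidedness are not stated; two-sided 0.05 is assumed here. With a Sobel test and all three correlations at .30:

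- a = .30; b = (.30 − .30 × .30)/(1 − .30²) = .21/.91 = .2308
- R² = (.09 + .09 − 2 × .027)/.91 = .1385
- SE(a) = √(.91/223) = .0639; SE(b) = √(.8615/(.91 × 222)) = .0653
- z = ab/√(a²·SE(b)² + b²·SE(a)²) = 2.82; power = Φ(2.82 − 1.96) = 0.806

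This agrees with 0.81. The calculation uses the ECAS sample alone, so the comparator's make-up does not enter it.

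**2. Who can be in each sample.**

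| Person | ECAS condition | Comparator |
|---|---|---|
| Essex resident, in page and group | yes | no |
| Essex resident, in neither, recalls no exposure | no | yes |
| Works in Essex, lives elsewhere, recalls no exposure | no: the group checks residence | yes: work limb |
| Works in Essex, lives elsewhere, follows the page only | no: group membership also required | no, on the text description of the comparator |

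The third row is the mismatch. The fourth row shows that access to the public page does not remove it: following the page alone does not qualify for the ECAS condition, and the text description keeps page followers out of the comparator.

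**3. Illustrative size.** The documents give neither the share of work-only comparators (f) nor their difference from residents (d, in SD). Both are assumed.

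- SE of the contrast = √(1/225 + 1/225) = √(2/225) = 0.0943 SD
- Shift = f × d
- Rejection rate with no ECAS effect, two-sided 5% normal test = Φ(−1.96 + shift/SE) + Φ(−1.96 − shift/SE)

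| f | Number of 225 | d | Shift (SD) | Shift/SE | Rejection |
|---|---|---|---|---|---|
| 10% | 22.5 | 0.2 | 0.02 | 0.21 | 5.5% |
| 20% | 45 | 0.3 | 0.06 | 0.64 | 9.8% |
| 30% | 67.5 | 0.4 | 0.12 | 1.27 | 24.7% |

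For scale, 225 per group detects about (1.96 + 0.84) × 0.0943 = 0.26 SD with 80% power.

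**4. Whether weighting would deal with it.** If residence were recorded and comparators were weighted to the ECAS profile, work-only respondents would get weights near zero, because that profile holds almost none. They would in effect be dropped after taking up places. With 30% dropped, 157.5 comparators remain and the SE becomes √(1/225 + 1/157.5) = 0.104. With 10% dropped, 202.5 remain and the SE becomes √(1/225 + 1/202.5) = 0.097.

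**The case against.** A reader might infer that work-only respondents could never have joined ECAS, or were not eligible for the intervention. The protocol does not support that. The postal-code check is described only for the private group. A non-resident could follow the page, and ECAS also presented information on Instagram and Twitter. What such a person could not do is meet the survey's definition of the ECAS condition.

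A reader might also infer that every ECAS respondent was a resident. The check is a request for a postal code at joining, with no proof of address or later check described, while the survey criterion refers to the first lockdown. Someone who worked in Essex then and moved there before joining would enter the ECAS sample through the work limb. Few or none is the accurate description.

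On mitigation, the demographic variables are not listed, so residence is not ruled out as a matching or weighting variable, and the representativeness check could lead to weighting. That is fair, but the check is conditional and neither provision names residence.

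On mechanism, the documents do not say that work-only people helped in some other community. Two of the three community champion items in Table 1 are online, and digital health literacy is not tied to place. The direction of any bias is therefore unknown.

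Finally, the powered analysis is untouched. The between-group comparison is a further analysis of convenience samples that will differ in other ways too. This narrows the point without removing it: unlike most such differences, this one is created by the wording of a criterion and can be removed before recruitment.

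**Conclusion.** The mismatch follows from the protocol's own text. The comparator can contain people who work in Essex, live elsewhere and could not have met the ECAS-condition definition; the ECAS sample will contain few or none. No stated balancing step names residence. The ECAS-versus-comparator contrast and the economic comparison are affected. The mediation models within ECAS users and the 0.81 power are not.

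The size is not known. The range of 0.02–0.12 SD, with rejection rates of 5.5% to 24.7% when ECAS has no effect, rests wholly on the assumed shares and gaps. The lower end is practically nominal, and the upper end needs both assumptions at their maximum. If few respondents only work in Essex, the effect will be small. The text does not show that the comparison is biased in a known direction or by a known amount. It shows an avoidable route to bias that is cheap to close.

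**What to change.** Ask both samples whether they lived in Essex in the reference period; the outward part of the postcode is enough. Then do one of the following:

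- change the criterion so that both samples must have lived in Essex in that period; or
- keep work-only respondents, but outside the 225 comparators, and restrict the main between-group and economic contrasts to residents.

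Screening at entry is better than weighting afterwards, for the loss of precision shown in the working. The cost is one screening question and one line of protocol text, with a slightly smaller pool of comparators to recruit from. The protocol is dated July 2021 and Milestones has survey data collection completing in November 2021, so the question has to be in the survey from the start: the difference cannot be recovered later if residence was not asked.
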